3.2 Subjects

The targeted study population consists of the entire Arizona population 15+ years of age. According to the ADHS 2017 vital statistics, this age range makes up 80% of the population and a total of 5,606,808 people. The targeted population is divided and ordered as below based on two parameters: known hepatitis C prevalence rates and risk, and the optimal method of communication.

1. Adults (45+)

Baby boomers are 5 times more likely to have hepatitis C than adults from any other age group⁴. According to AZ DHS population statistics, this group makes up 51% of the targeted population; 2,864,689 people. We hypothesize that older people are not exposed to social media as adolescents and young adults are. Therefore, it is important to utilize Email, direct text messages and newspaper outreach to reach this population.

2. Nasal and Injection Drug Users

Another extremely high-risk subgroup is nasal and injection drug users. Figure 5 below shows the rate of HCV positive antibody tests compared to the percentage tested categorized by risk factors. The results indicate 88% of the HCV positive clients had history of nasal drug use compared to 69% amongst all clients¹. We believe reaching out to this community would be an essential step in diminishing hepatitis C. To reach out to this group we plan on distributing pamphlets to treatment and rehabilitation entities.

3. Homeless

Another high-risk subgroup likely to develop infectious diseases is the homeless. According to Phoenix Rescue Mission, there are over 36,000 homeless people in Arizona, 71% of which are in Maricopa county⁸. In addition to their lack of awareness, this group likely do not have access to healthcare or healthy living environments, making them even more prone to fatal viruses and diseases. The most appropriate method to reach this subgroup would be through homeless shelter visits.

4. Adults (20-44)

This age groups makes up about 40% of the targeted population; 2,273,230 people. This group is likely exposed to social media as well as newspapers and direct communication methods such as email and text messages.

5. Millennials / Adolescents (<19 years of age)

We believe this age group, consisting of 8% of the targeted population; 468,889 people, would be equally responsive to social media and directed Emails and text messages. With the growing impact social media has on this category, it has more potential of engaging them than any other means of communication would.

3.3 Educational Outreach

The systemized approach that will be taken in this study will target all patients repeatedly through a series of methods starting with individuals of higher risk, priority and expected response rate. Outreach program will follow AZ HCV prevalence map (Figure 4), starting from high prevalence counties with 123 or more Hepatitis C cases per 100,000, medium prevalence areas with 101-123 cases per 100,000 and finally low prevalence counties with less than 101 cases per 100,000¹.

3.4 Population Screening

Screening Promotion

A time limited screening test promotion code, specific to educational outreach methods, will be obtained from Sonora Quest Laboratories and advertised in both direct and indirect communication methods of the educational program. Interested individuals would be required to present a specific promotional code and sign the Informed Consent Form.

Screening Locations

Screening will take place in all branches of Sonora Quest Laboratories over the state of Arizona. Patients will have the opportunity to present at any of the locations and get free screening regardless of their insurance coverage or whether they are considered at risk or not.

Informed Consents

The study, expectations and rights will be explained to patients. Informed consents will be obtained electronically by the screening team to perform anti- HCV test, to share personal information and test result with Liver Institute study investigator team, and to agree to discuss treatment options if HCV test become positive. Consents will be sent to the Liver Institute PLLC where they will be stored in an encrypted electronic data capture system as per Western Institutional Review Board (WIRB) guidelines.

Clinical Parameters

Demographics data and contact information will be recorded for each patient in Sonora Quest Laboratories data system as per their guidelines. Clinical and relevant history pertaining to hepatitis C including diabetes and existing conditions will be collected by study team from HCV positive individuals.

LI-HEPC-AZ V1.0 CONFIDENTIAL ➢ Screening

Screening will be conducted by members of the Sonora Quest Laboratories with ELISA IV antibody test with reflex to HCV PCR test to confirm the diagnosis. Patients will be contacted with their test results by a member of the research team, as well as by Sonora Quest.

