The study will focus on various methods of communication to reach the **Methods:** population of Arizona from the most prevalent counties to lowest prevalence. The study is organized into phases focusing on the various communication methods beginning with direct communication through mass text messages and mass emails followed by indirect communication through social media (YouTube, Facebook), newspaper, radio, Alcoholics Anonymous meetings, Narcotics Anonymous meetings, and homeless shelters. Each phase will consist of four cycles of a monthly intervention period in which communication will be active and a two-month gap that will be used to assess effectiveness of the communication method. Subjects will receive information on HCV, contact information for the study coordinator at the Liver Institute PLLC to address questions or concerns, and a code that will allow them to receive a free HCV screening test at their local Sonora Quest Lab. This code can be used at the time of receipt or a few months later, whenever the subject is ready for testing. This timeline allows to enhance subject compliance. The results from Sonora Quest Lab will be transmitted to the study coordinator at the Liver Institute PLLC and depending on the subject's insurance status will link the subject to a treatment center. Ideally it will be their primary care physician but if the subject does not have one then it will be the closest treatment center. Alternatively, the Liver Institute PLLC is also equipped to provide telemedicine appointments to evaluate the subject and provide treatment depending on insurance status. Those that are uninsured will be provided with available options for treatment. All subjects will receive information on the disease to reduce transmission and encourage friends/family to get tested. This study will function on a version of the test-and-treat approach to help reduce the spread of HCV in the Arizona population. **Results:** The study will allow us to obtain diagnostic rates for each communication method as well as the number of HCV positive individuals that are linked to care for treatment. By comparing diagnostic rates between communication methods, we can identify the most successful method to utilize for a bigger subject outreach. Additionally, by determining the rates of HCV positive individuals linked to care, we can identify deficits in the treatment of screened individuals. These components taken together will allow us to evaluate the overall success of our study.

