Email listings of Arizona residents will be obtained from National Data Group and mass emails will be sent through sendgrid.com.

b. Frequency and Resources

Emails will be sent out daily during intervention periods of 2 months followed by a 1month gap for two rounds for each of the different prevalence groups. A project coordinator at the Liver Institute PLLC will assure expectations and targeted numbers are met.

c. Email Content

The email content will follow the template in Appendix 8.1, including an introduction of the program coordinator, introduction to the project as well as brief background information on

the disease and its risk factors (Appendix 8.6). It will also include the steps that need to be taken and contact information to answer any questions.

d. Progress Monitoring

Updates will be obtained from the carrier company as documented proof of the number of emails sent. Information will also be collected on how many emails were rejected and how many were opened. This information will then be used to guide adjustments of upcoming steps if expected response rates are not reached.

2. Direct Text Messages

Response rates to text messages are similar to that of emails at about 2% or 112,136 of the targeted population.

a. Generating Phone List

A list of Arizona residents phone numbers will be generated by National Data Group and messages will be sent to the targeted population through Verizon wireless.

b. Frequency and Resources

Text messaging will similarly follow the protocol described in Figure 3. Messages will be sent daily during the intervention period for 2-month followed by a 1-month gap for two rounds for each of the different prevalence groups.

c. Text Content

The text content will follow the template in Appendix 8.2. The message will be brief in comparison to the email content. It will include an introduction of the program coordinator, introduction to the project, the steps that need to be taken to get screened and a link to more information and background on the disease. It will additionally include contact information to answer any questions or connect to screening and treatment resources.

d. Progress Monitoring

Updates will be obtained from the carrier companies as to how many messages were sent daily and how many were rejected. This information will then be used to guide further changes or alterations if expected response rates are not reached.

Phase 2: Indirect Communication

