5.0 Data Management and Analysis

- 5.1 Data Entry and Management
 - >Data will be entered into the electronic data capture system utilized by the Liver Institute PLLC.
 - >Data and results will be entered within a week after they are collected during the mid-study and end-of-study data collection phases.
 - >Data will be de-identified prior to analysis
- 5.2 Data Analysis
 - > A statistician will overlook and conduct final data analysis
 - > Data will be analyzed for trends at the end of the study
 - > Analysis will be completed using IBM SPSS statistics version 24
- 5.3 Results
 - Assuming similar response as obtained for breast cancer or cervical cancer projects, we expect 4% of the targeted population to respond.
 - Based on the prior data, we computed the trend of increase in number of new HCV patients added per year to the pool of diagnosed cohort.
 - According to mapping hep C¹¹, the total number of Antibody screening tests performed in 2016 is 53,580, or 4,465 per month, which is expected to be like current rates of 2019.
 - > We estimate that similar number of subjects will come for self-screening
 - We expected to, at minimum, double the number of screenings to 8,930 tests per month, which will be evaluated after each intervention period as defined in Figure 3. This increase will correlate with the increase in diagnosis rates per 100,000 from 776 to at least 1,552. These numbers will be used as measures of success for the project.
 - Assuming the current rate of 5.2% positive HCV tests holds, we expect at least 464 people to be HCV+ per month from the 8,930 people screened.
 - ➢ From the total number of HCV positive individuals, only 26.1% in Arizona get treatment, which correlates with 120 people per month from the screened population or total of 1440 by the end of the study. Considering there are multiple challenges to treatment and complete eradication, the goal of the study is to promote treatment for those with access to healthcare; expecting to increase treatment rate to about 30%.
 - Statistical data and trends of HCV prevalence over previous years, obtained from the Arizona Department of Public Health, will be compared with the study outcomes to assess the success rate of the study. we expect the number of screened individuals to double and the diagnosis rate to remain at 5.2%. A measure of success is therefore defined as 8,930 or more screening tests performed per month.

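### The promotional code has no stated expiry and no stated round, so tests prompted by one outreach round can be counted in a later round's window

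*Protocol*

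**What the plan says.** **What the code identifies.** Protocol Section 3.4 (Screening Promotion) provides for "A time limited screening test promotion code, specific to educational outreach methods". Method is the only identifier named. The code is limited in time, but no limit is given.

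**When it may be used.** The synopsis (Methods) states: "This code can be used at the time of receipt or a few months later, whenever the subject is ready for testing".

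**How the rounds run.** Section 3.1, on email: "Emails will be sent out daily during intervention periods of 2 months followed by a 1month gap for two rounds". Text messages, newspapers, YouTube and radio follow the same pattern, "for two rounds for each of the different prevalence groups". The synopsis describes the cycle differently: one active month and a two-month gap. Either way a cycle lasts 3 months. In Phase 1 the three prevalence tiers occupy months 1-6, 7-12 and 13-18, with no break between them.

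**When results are judged.** Section 5.3 sets a target of doubled monthly screening, "which will be evaluated after each intervention period as defined in Figure 3". For newspapers and for shelter visits, Section 3.1 bases monitoring or impact on screening seen in the gap periods. For several methods it also provides for adjustments during the study.

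**The success measure.** Section 5.3: "A measure of success is therefore defined as 8,930 or more screening tests performed per month".

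**The concern.** A 3-month cycle, a code that may be redeemed some months after receipt, and an evaluation after every intervention period fit together only if each test can be traced to the round that prompted it. The text offers the method and the test date. If tests are assigned by date, a late test from round 1 is counted in round 2, and a late test from round 2 falls in the calendar window of the next tier. Two equally effective rounds would then look unequal, with the first too weak and the second too strong.

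What is at stake is the estimate of response per round and any decision to change the outreach that rests on it. The point cannot be left to an analysis plan. Once identical codes have been sent out in both rounds, the round of origin is lost and no later analysis can restore it.

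**Working it through.** **1. The plan's own figure.** Section 5.3 states that "the total number of Antibody screening tests performed in 2016 is 53,580, or 4,465 per month". 53,580 / 12 = 4,465, and 2 x 4,465 = 8,930. The threshold reproduces. It is a count of tests by the month in which they are performed.

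**2. Inputs for the carry-over.**
- Body schedule (Section 3.1): 2 active months, 1 gap month.
- Synopsis schedule: 1 active month, 2 gap months.
- Redemption delay: not in the protocol, so a range is assumed.
- Further assumptions: messages spread evenly over the active months, and no expiry inside the range considered.

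**3. Fixed delay of L months.** The share of a round's tests that fall after its own 3-month cycle is:
- Body: (L - 1)/2 for L from 1 to 3. This gives 0%, 50% and 100% for L = 1, 2 and 3.
- Synopsis: L - 2 for L from 2 to 3. This gives 0%, 50% and 100% for L = 2, 2.5 and 3.

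**4. Exponential delay with mean m months.** Averaging exp(-(3 - t)/m) over the sending time t gives the share s:
- Body (t from 0 to 2): s = 0.5 x m x [exp(-1/m) - exp(-3/m)]
- Synopsis (t from 0 to 1): s = m x [exp(-2/m) - exp(-3/m)]

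For example, with m = 2 on the body schedule, s = 0.5 x 2 x (0.6065 - 0.2231) = 0.383.

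| Mean delay (months) | After own cycle, body | After own cycle, synopsis |
|---|---|---|
| 0.5 | 3% | 1% |
| 1 | 16% | 9% |
| 2 | 38% | 29% |
| 3 | 52% | 44% |

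**5. How two equal rounds would look (body schedule, counted by date).** Round 1's window keeps 1 - s. Round 2's window holds its own 1 - s plus the round-1 tests that fall in months 3 to 6, which are s x [1 - exp(-3/m)]. The apparent ratio of round 2 to round 1 is

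1 + s x [1 - exp(-3/m)] / (1 - s)

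- m = 1: 1 + 0.159 x 0.950 / 0.841 = 1.18
- m = 2: 1 + 0.383 x 0.777 / 0.617 = 1.48
- m = 3: 1 + 0.523 x 0.632 / 0.477 = 1.69

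**6. Tier windows, if tests are counted by date.** Averaged over a tier's two rounds, the share after the 6-month block is s x [1 + exp(-3/m)] / 2. On the body schedule this is 8%, 23% and 36% for m = 1, 2 and 3. This loss is avoidable where county of residence is used instead of the date.

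**7. Effect of an expiry.** If codes lapse at the end of the gap month, every share above is zero, but the code can then hardly serve someone who wishes to use it some months after receipt. If the expiry is long enough to honour the synopsis, carry-over is possible.

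**The case against.** A reader might infer more than the protocol supports. Four stronger readings fail.

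- **That the success measure is biased.** It is not. The 8,930 threshold counts tests in the month performed, against a baseline of the same kind. A late redemption belongs to the month in which it occurs, and no attribution to a round is needed.
- **That the comparison of methods is biased.** The synopsis announces a comparison between communication methods, and a method-specific code serves it. Carry-over within a method moves tests between periods and leaves the method's total unchanged. No objective or endpoint in Section 2 compares rounds.
- **That tests will be credited to the wrong tier.** No rule to credit by test date is stated for tiers. Contact information is recorded for each patient (Section 3.4), so county of residence gives the tier for email and text. The test site does not, because any branch in the state may be used.
- **That the code is fixed as carrying the method and nothing else.** The text does not exclude a new code for each run, and a time-limited code may have to be renewed over 45 months. Figures 3 and 6 are not in the text available here and might say more.

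It is also fair to object that round-specific codes do not rescue an adjustment made straight after round 1, because the late tests have not happened yet. Nor is the code a perfect marker: messages go out daily in both rounds, and someone contacted in both may present either code.

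All of this stands, and it confines the point to estimates of response per round. It does not remove it. Method is the only identifier that Section 3.4 names, the expiry is unstated, and nothing in the text recovers the round.

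**Conclusion.** The point holds as a modest and cheap improvement. Three provisions do not fit together: a time-limited code with no stated limit, redemption allowed some months after receipt, and evaluation after each round of about 3 months with no washout. Tests prompted by one round can be counted in a later one.

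The size depends on a redemption delay that the protocol does not give. With mean delays of 1 to 3 months and no intervening expiry, about 16% to 52% of a round's tests fall after its own cycle on the body schedule, and 9% to 44% on the synopsis schedule. If most people redeem quickly (mean 0.5 month), the share is about 3% on the body schedule and the matter is minor. Only response per round, and tier results if these are counted by test date, are exposed.

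**What to change.** In Section 3.4:
- Issue codes specific to method and round, adding prevalence tier for email and text. For statewide media, use method and run period.
- State the code's expiry and reconcile it with the synopsis. The two descriptions of the cycle (2 + 1 and 1 + 2 months) should be reconciled at the same time.

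In Section 5.3, report response per round by code of origin. This supplements the monthly count of tests performed and does not replace it.

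**Cost.** About 33 code strings: 2 direct methods x 3 tiers x 2 rounds = 12, 3 media x 6 run periods = 18, and 3 for the shelter and meeting visits. Method-only codes would need about 6 (2 + 3 + 1). The same laboratory supplies them. The change has to be made before codes are issued.

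**Downsides.** A round's count is final only when its code expires, so adjustments made directly after a round still rest on incomplete counts. People contacted in both rounds may present either code, so the code of origin remains an approximation to the message that prompted the test.

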3.5 Links to Care: Treatment of HCV Infection

- In case of a positive test results, the project coordinator will communicate with the patients for treatment options.
- Patients with HCV+ screening results will be contacted during the gap periods by the program coordinator, who will link these patients to treatment and care.
- Project coordinator will identify HCV care provider for each HCV positive patient depending upon patient's insurance status.
- Project coordinator will help and facilitate assistance program applications to patients without insurance.
- > The screening process is shown in Figure 6.

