3.0 Investigational Plan

3.1 Study Design

- This is a prospective study performed over a 45-month period. The principal design plan will follow Figure 3 below.
- The study design is based on HCV prevalence order, which was determined based on statistical data from the Arizona Department of Health Services and rate of Hepatitis C per 100,000 (Figure 4). High prevalence counties (123+ cases per 100,000) including La Paz, Mohave, and Yavapai with a total targeted population of 391,999 individuals. Medium-prevalence Counties (101-123 cases per 100,000) are Coconino, Gila, Greenlee, Maricopa, Pima and Pinal with total targeted population of 4,724,421. Low-prevalence counties (<101 per 100,000) including Apache, Cochise, Graham, Navajo, Santa Cruz, and Yuma with a population of 490,388.

- For the initial 9 months the study will utilize direct communication methods (email and text messages) to reach high prevalence areas (Month 1-6), medium prevalence areas (Months 7- 12), and low prevalence areas (Month 13-18).
- The second phase of the study will utilize indirect communication methods (Newspapers and Radio advertisements) and similarly target areas of high prevalence (Month 12-24), medium prevalence (Month 25-30) and low prevalence (Month 31-36).
- The third and last phase is detected for shelter visits and homeless education in high prevalence areas (Month 37-39), mid-prevalence areas (Month 40-42) and low prevalence areas (Month 43- 45).
- This program will follow a streamline cascade of care with three complementary, consecutive portions: Patient education during intervention periods, connection to appropriate care and treatment during gap periods (Figure 3).
- The person responsible for conducting and implementing the project will be the program coordinator. The coordinator will be responsible for responding to calls or emails regarding the study in reference to the FAQ in Appendix 8.3. One hour daily, 5 days per week will be dedicated to answering emails and responding to voice messages or calls. The number of hours will be adjusted according to project performance and needs.

Phase 1: Direct Communication

1. Direct Customized Email Messages

Email messages are customizable and tailored to individual people. The expected response rate as compared to similar healthcare content is about 2%, 112,136 of our targeted group.

a. Generating Email List

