1. Newspapers, Advertisement Content, and Duration

Newspaper advertisements are assumed to generate a response rate of 2% or 112,136 of the targeted population. However, according to the local newspaper statistics, the response rate is expected to be higher.

a. Newspapers

The most common local newspaper in Arizona is The Arizona Republic. Both newspapers are well-rounded, published daily or weekly and readily available to the public. This newspaper serves all counties in Arizona, making it efficient and more accessible to all members of the population.

The Arizona Republic – Best Life

According to republic media.com, "Best Life" is the section inside the Arizona Republic dedicated for active, healthy adults and include preventative health tips and postings. This section is published weekly on Mondays and typically generates 46% response rate from the reader population.

The Arizona Republic – Overview

Since the previous section focuses on health-conscious individuals, another post will be published in the overview section, which is distributed daily. According to republicmedia.com, this section reaches 1.1. million adults weekly in the Phoenix area, 32% of local residents. Advertising through the Arizona Republic is therefore likely to generate the expected response rate and reach the majority of our targeted population.

- b. Duration and Monitoring
 - The hepatitis C newspaper advertisement will run similarly to other communication methods during the intervention periods; in 2-month intervals followed by 1-month gap for two rounds for each of the different prevalence groups.
 - Data collection and monitoring will be based on screening numbers during the gap periods. The project coordinator will be responsible for communicating with the magazine to make adjustments as needed.
- c. Advertisement Content
 - The content of the newspaper advertisement will be an infographic designed to present background information on the disease, a brief explanation of the program and its rationale and next steps that need to be taken.
 - The infographic will be designed by the program coordinator to display the information in a simple and clear format to comply with the newspaper's requirements.

2. Social Media

The third approach aimed to target the remaining 33%; 835,414 is social media: including radio and YouTube advertisements. This method is expected to generate a response rate of about 2%.

a. YouTube ➤ Type of Advertisement

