7.0 Discussion and Expected Challenges

- Several challenges stand in the way towards complete Hepatitis C eradication. In addition to lack of public awareness leading to low screening percentage, only about 26.1% of the HCV+ population receive treatment.
- During the gap periods of the study the project coordinator will communicate with patients and providers to facilitate the process of treatment. However, several challenges like insurance and access to healthcare might not be inevitable, making it unlikely to increase the treatment rate significantly. On the other hand, the total number is expected to proportionally increase with the number of screened individuals.
- Increasing the public awareness will likely result in a sustained increase in screening rates and gradual improvement in treatment availability and access. Therefore, and through utilizing more efforts the treatment rates can be expected to increase over the upcoming years, moving closer towards our goal of HCV eradication.

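### Linkage to care for HCV-positive people is scheduled in the gap periods, so on the Phase 1-2 cycle it may wait up to 2 months

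*Protocol*

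**What the plan says.** Three sections of the Protocol place contact and linkage in the gaps:

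- Section 3.5, second bullet: "Patients with HCV+ screening results will be contacted during the gap periods by the program coordinator". The same sentence makes that coordinator responsible for linking them to care.
- Section 3.1, on the cascade of care: "three complementary, consecutive portions: Patient education during intervention periods, connection to appropriate care and treatment during gap periods".
- Section 7.0: "During the gap periods of the study the project coordinator will communicate with patients and providers to facilitate the process of treatment".

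Two places name a trigger and no time:

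- Section 3.5, first bullet: "In case of a positive test results, the project coordinator will communicate with the patients for treatment options".
- The Synopsis (Methods) sends laboratory results to the study coordinator who, "depending on the subject's insurance status will link the subject to a treatment center".

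The cycle is set in Section 3.1. For email: "Emails will be sent out daily during intervention periods of 2 months followed by a 1month gap for two rounds". Text messages, newspaper, YouTube and radio follow the same pattern. The Synopsis instead describes one active month and a two-month gap, four times per phase.

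Notification of the result is separate. Section 3.4 states: "Patients will be contacted with their test results by a member of the research team, as well as by Sonora Quest". Section 3.1 also gives the coordinator an hour a day, five days a week, for calls and emails. No section sets a maximum time from a positive result to linkage.

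**The concern.** The sentences that give a time for linkage all point to the gap. A site that follows them would hold a person found positive in an active period until outreach pauses. The wait would then depend on the outreach calendar and not on anything clinical.

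The Synopsis calls the study a version of test-and-treat, the third objective in 2.1 is to evaluate the central linkage system, and patients treated is a primary endpoint in 2.2. Section 5.3 hopes to raise the treatment rate from 26.1% to about 30%. A built-in wait between result and linkage works against each of these. Staff who read the two bullets of 3.5 differently could also handle positives unevenly.

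**Working it through.** **1. Which cycle is operative.** Inputs from Section 3.1: 2 active months plus 1 gap month, two rounds per prevalence tier, three tiers, and 3 months per tier in Phase 3.

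- Per tier in Phases 1 and 2: 2 × (2 + 1) = 6 months.
- Per phase: 3 × 6 = 18 months.
- Phase 3: 3 × 3 = 9 months.
- Total: 18 + 18 + 9 = 45 months, which is the stated study length.

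The phase end points printed in 3.1 (Months 18, 36 and 45) agree. That section also prints an initial 9 months for Phase 1 and Month 12-24 for the first Phase 2 tier. These do not fit the other windows, but they do not affect the 2+1 pattern.

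The Synopsis cycle gives 4 × (1 + 2) = 12 months per phase, and 3 × 12 = 36 months for three phases. It does not reproduce 45. The body's cycle is therefore the better basis.

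**2. The wait.** Let A be the active length, G the gap length and t the time of the positive result within the cycle. If linkage starts at the next gap, the wait is A − t when t < A, and 0 when the result falls in the gap. For results spread evenly over the cycle (an assumption), the mean is A/2 for results in active months and (A²/2)/(A + G) for all results.

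| Cycle | Maximum wait | Mean, results in active months | Mean, all results |
|---|---|---|---|
| Body, A = 2, G = 1 | 2 months | 1.0 month | 2/3 = 0.67 month |
| Synopsis, A = 1, G = 2 | 1 month | 0.5 month | 0.5/3 = 0.17 month |

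If linkage starts on receipt of the result, the calendar adds no wait. The maxima need no assumption about how results are spread; the means do. Phase 3 gives no split between active and gap time within its 3-month tiers, so no figure is given for it.

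**3. Whether the gap's assessment needs the wait.** The Synopsis uses the gap to judge the communication method. For newspapers, Section 3.1 states: "Data collection and monitoring will be based on screening numbers during the gap periods". Phase 3 measures impact by screening and test results. Linkage comes after the test, so the person's screening is already counted. Linking that person sooner leaves the count as it was.

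**The case against.** The strongest case on the other side is that this is operational wording. No sentence restricts contact to the gaps alone. Patients are told their results under 3.4 with no tie to the gap, and they can call the coordinator. The email template in 8.1 and the FAQ in 8.3 promise links to care without mentioning gaps. Section 3.1 assigns connection to care to the gap as one stage of the cascade, so the gap has that role by design, and batching the work may suit a single coordinator. Figures 3 and 6, which may settle the timing, were not in the text available.

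Much of this stands. It softens the delay and limits how firmly it can be stated. But being told a result is not the same as being matched to a provider by insurance or helped with an assistance application, and no text lifts the gap timing.

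Three stronger readings are tempting, and the Protocol does not support them.

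- **That the two bullets of 3.5 contradict each other.** They do not: the first gives a trigger and the second a time, and they can be read together.
- **That a known number of people would wait.** From the target in 5.3, a reader might take the added tests, 8,930 − 4,465 = 4,465 a month, times 5.2% = 232 positives a month, and so 2 × 232 = 464 waiting per 3-month cycle. That treats a target as a flow and applies a statewide figure to every tier, although the high-prevalence tier holds 391,999 of 5,606,808 people, about 7%. It also assumes that results arrive evenly and that every positive antibody test is confirmed. The Synopsis lets codes be used months later, so the share of results in active months is unknown.
- **That patients treated will fall by a stated amount.** No loss rate is given, and the endpoint has no time window.

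**Conclusion.** The point holds as a scheduling rule that should be changed. Sections 3.1, 3.5 (second bullet) and 7.0 put linkage in the gap periods, and the untimed trigger elsewhere does not override them. Followed as written, linkage may wait from 0 to 2 months in Phases 1 and 2, or from 0 to 1 month if the Synopsis cycle were used. This rests on reading the timed sentences literally and on the 2+1 cycle, which reproduces the 45 months. The delay concerns the coordinator's contact and linkage, not notification of the result. It may lower patients treated, but neither the effect nor the number of people affected can be fixed from the Protocol. Confidence is moderate, because Figures 3 and 6 could not be seen.

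**What to change.** - In the second bullet of 3.5, replace the gap-period timing with: on receipt of the confirmed positive result, within a fixed number of days set by the sponsor, in any study period, including after the last gap. Deleting the gap wording alone would leave no timing anywhere.
- In 3.1, remove the gap-period timing and the word 'consecutive' from the sentence on connection to care.
- In 7.0, remove the gap-period timing.
- Keep the gaps for assessing screening numbers, and bring Figures 3 and 6 into line.

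The cost is a wording change in three sentences and a check of two figures. Some coordinator time moves into the active months. The number of people to contact does not change, and 3.1 already allows the hours to be adjusted. Whether staffing is sufficient could not be checked, because the resource table under 8.5 was not in the text available.
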